### 5.7.4 Criteria for Defining the Severity of an Adverse Event

All AEs, including abnormal clinical laboratory values, will be graded using the National Cancer Institute (NCI)-Common Terminology Criteria for Adverse Event (CTCAE) guidelines (Version 4.03).

#### 5.7.4.1 Study Specific Ocular Toxicity Grading Criteria

Refer to Section [5.6.5](#)

### 5.7.5 Reporting Procedures for All Serious Adverse Events (SAEs)

All SAEs occurring after the first dose of investigational product observed by the investigator or reported by the subject (whether or not attributed to investigational product), will be reported to the sponsor. SAEs considered related to the investigational product by the investigator or the Sponsor will be followed until resolved or considered stable.

All SAEs that occur up to the last formal follow-up observational period, must be reported  $\leq 1$  working day of discovery or notification of the event.

In the case of a SAE, the investigator must contact the sponsor by fax or email immediately (within 24 hours of awareness).

The investigator must complete and submit a SAE worksheet containing all information that is required by local and/or regional regulations to the sponsor by email or fax immediately (within 24 hours of awareness).

For contact details, see [Section II Contact Details of Key Sponsor's Personnel](#). Fax or email the SAE Worksheet to:

Astellas Pharma Global Development, Inc.  
Pharmacovigilance  
[contact]  
Alternate North America [contact]  
Email: [[contact]](mailto:[contact])

The investigator should notify the IRB/IEC/REB of SAEs occurring at the site and other AE reports received from Sponsor, in accordance with local requirements and procedures.

If there are any questions, or if clarification is needed regarding the SAE, please contact the Sponsor's Medical Monitor/Expert or his/her designee (see [Section II Contact Details of Key Sponsor's Personnel](#)).

The SAE form should be completed with all available information but at the very bare minimum the following information is required for a case to be valid:

- Identifiable subject (Subject number)
- Identifiable reporter (e.g., investigator)
- A description of the SAE, and
- Suspect drug

In addition to the above 4 critical information to establish a valid case, the following information is needed to assess the regulatory reporting requirement and Sponsor's causal attribution:

- Causality
- Event description
- Event onset date
- Study drug treatment dates

Post initial SAE report submission, the investigator will promptly submit any relevant information that becomes available (e.g., information that impacts causality, changes event outcome, changes event severity).

The Sponsor or Sponsor's designee will submit, as necessary, expedited safety reports (i.e., SUSAR [Suspected Unexpected Serious Adverse Reaction report]) to the pertinent regulatory agencies in the appropriate format according to International Conference on Harmonization (ICH) guidelines and applicable country-specific legal requirements, and will inform the investigators of such regulatory reports. Investigators must submit safety reports as required by their Institutional Review Board (IRB)/Independent Ethics Committee (IEC).

Documentation of the submission to and receipt by the IRB/IEC must be retained by the site.

The Sponsor will notify all investigators of all expedited safety reports from all ongoing clinical studies with AGS-16C3F.

You may contact the Sponsor's Medical Monitor or IRB/IEC, depending on the nature of issue, for any questions related to subject safety, welfare, and/or rights.

### 5.7.6 Follow-up of Adverse Events

SAEs and medically significant AEs considered related to the investigational product by the investigator or the Sponsor will be followed until resolved or considered stable.

If a treatment-related adverse event is not resolved but is considered stable at the safety follow-up visit, this must be documented in the source documents.

Please refer to Appendix [12.2](#) for detailed instructions on Drug Induced Liver Injury (DILI).

### 5.7.7 Monitoring of Common Serious Adverse Events

Common serious adverse events are SAEs commonly anticipated to occur in the study population independent of drug exposure. SAEs classified as “common” are provided in Appendix [12.3](#) for your reference. The list does NOT change your reporting obligations or prevent the need to report an AE meeting the definition of an SAE as detailed above. The purpose of this list is to alert you that some events reported as SAEs may not require expedited reporting to the regulatory authorities based on the classification of “common SAEs” as specified in Appendix [12.3](#). The Sponsor will monitor these events throughout the course of the study for any change in frequency. Any changes to this list will be communicated to the participating investigational sites. Investigators must report individual occurrences of these events as stated in Section [5.7.5](#).

### 5.7.8 Procedure in Case of Pregnancy

If a female subject or partner of a male subject becomes pregnant during the study dosing period or  $\leq 6$  months from the discontinuation of dosing, the investigator should report the information to the Sponsor as if it is an SAE. The expected date of delivery or expected date of the end of the pregnancy, last menstruation, estimated conception date, pregnancy result and neonatal data etc., should be included in this information.

The investigator will follow the medical status of the mother, as well as the fetus, as if the pregnancy is an SAE and will report the outcome to the Sponsor.

When the outcome of the pregnancy falls under the criteria for SAEs (spontaneous abortion, induced abortion, stillbirth, death of newborn, congenital anomaly [including anomaly in a miscarried fetus]), the investigator should respond in accordance with the report procedure for SAEs. Additional information regarding the outcome of a pregnancy (which is categorized as an SAE) is mentioned below.

- “Spontaneous abortion” includes miscarriage, abortion and missed abortion
- Death of an infant within 1 month after birth should be reported as an SAE regardless of its relationship with the study drug
- If an infant dies more than 1 month after the birth, it should be reported if a relationship between the death and intrauterine exposure to the study drug is judged as “possible” by the investigator
- In the case of a delivery of a living newborn, the “normality” of the infant is evaluated at the birth

- Unless a congenital anomaly are identified prior to spontaneous abortion or miscarriage, the embryo or fetus should be assessed for congenital defects by visual examination

### **5.7.9 Emergency Procedures and Management of Overdose**

The effects of overdose of this product are not known.

In the event of suspected AGS-16C3F overdose, the subject should be observed closely for signs of toxicity and as necessary and appropriate, receive supportive care. The Medical Monitor must be immediately notified of an overdose or a suspected overdose.

In the event of suspected overdose for axitinib, refer to the approved Package Insert, SPC, or local product information supplied by the manufacturer for the agent.

### **5.7.10 Supply of New Information Affecting the Conduct of the Study**

When new information becomes available necessary for conducting the clinical study, the Sponsor will inform all investigators involved in the clinical study as well as the regulatory authorities. Investigators should inform the IRB/IEC of such information when needed.

## **5.8 Test Drug Concentration**

Blood samples for the determination of serum AGS-16C3F concentrations will be collected according to [Table 2](#)

- Cycle 1, Day 1: predose (before the AGS-16C3F infusion), end of infusion (EOI), 4 hours, and Days 2 (24 hours), 4 (72 hours), and 15 (336 hours) post infusion
- Cycle 2, Day 22: predose (before the AGS-16C3F infusion)
- Cycle 3, Day 43: predose (before the AGS-16C3F infusion)
- Cycle 4, Day 64: predose (before the AGS-16C3F infusion), end of infusion (EOI), 4 hours, and Days 65 (24 hours), 67 (72 hours), and 78 (336 hours) post infusion
- Cycle 6, Day 106: predose (before the AGS-16C3F infusion)

Blood sampling, processing, storage and shipment instructions will be provided in the Lab Manual. Samples will be shipped to and analyzed by a Sponsor designated analytical laboratory. Please refer to the Lab Manual for more detailed information.

## **5.9 Total Amount of Blood**

The approximate amount of blood to be collected from each subject at each time point is for all laboratory assessments is included in Appendix [12.4](#)

# **6 DISCONTINUATION**

## **6.1 Discontinuation of Individual Subject(s)**

A discontinuation is a subject who enrolled in the study and for whom study treatment is permanently discontinued prematurely for any reason.

The subject is free to withdraw from the study treatment and/or study for any reason and at any time without giving reason for doing so and without penalty or prejudice. The

investigator is also free to terminate a subject's involvement in the study at any time if the subject's clinical condition warrants it.

If a subject is discontinued from the study with an ongoing AE or an unresolved laboratory result that is significantly outside of the reference range, the investigator will attempt to provide follow-up until the condition stabilizes or no longer is clinically significant.

The subject will be discontinued from treatment if any of the following occurs:

- Subject develops objective disease progression per RECIST v.1.1 criteria based on investigator assessment.
- Subject develops clinical progression (if objective disease progression is not evaluated).
- Subject develops a Grade 4 or unacceptable AE as assessed by the Investigator (Refer also to Section 5.6.2.1.3 and Section 5.6.5.2.1)
- Investigator decides that it is in the subject's best interest to discontinue.
- Subject declines further study participation (i.e., study withdrawal).
- A significant protocol deviation or non-compliance occurs with a subject that compromises study objectives or subject safety.
- Subject is lost to follow-up despite reasonable efforts by the Investigator to locate the subject.
- The study is terminated by the Sponsor.

The Medical Monitor must be contacted before a subject is discontinued from study treatment for reasons other than objective disease progression per RECIST v.1.1.

## 6.2 Discontinuation of the Site

If an investigator intends to discontinue participation in the study, the investigator must immediately inform the Sponsor.

## 6.3 Discontinuation of the Study

The Sponsor may terminate this study prematurely, either in its entirety or at any study site, for reasonable cause provided that written notice is submitted in advance of the intended termination. Advance notice is not required if the study is stopped due to safety concerns. If the Sponsor terminates the study for safety reasons, the Sponsor will immediately notify the investigator and subsequently provide written instructions for study termination.

## 7 STATISTICAL METHODOLOGY

The statistical analysis will be coordinated by the responsible biostatistician of Astellas. A Statistical Analysis Plan (SAP) will be written to provide details of the analysis, along with specifications for tables, listings and figures to be produced. The SAP will be finalized before the database soft lock at the latest. Any changes from the analyses planned in SAP will be justified in the Clinical Study Report (CSR).

Prior to Database Lock, a Final Review of Data and TLFs Meeting will be held to allow a review of the clinical trial data and to verify the data that will be used for analysis set classification. If required, consequences for the statistical analysis will be discussed and documented. A meeting to determine analysis set classifications may also be held prior to database lock.

In general, all data will be summarized with descriptive statistics (number of subjects, mean, standard deviation, minimum, median and maximum) for continuous endpoints, and frequency and percentage for categorical endpoints.

## **7.1 Sample Size**

For subjects with metastatic RCC that has progressed after at least 2 prior lines of therapy, a median PFS of 4 months is anticipated for the control agent. It is hypothesized that AGS-16C3F will improve median PFS in such subjects by 2 months (i.e., 4 vs 6 months). Under the assumption of exponential distribution of PFS, such an improvement corresponds to a hypothesized hazard ratio of 0.667. If this hypothesized hazard ratio is true, 110 PFS events provide 80% power to achieve a one-sided p-value of 0.1 or smaller. Such a result will be achieved when the observed hazard ratio is 0.783 or smaller; and the observed difference in median PFS is 1.1 months or larger if the observed median for the control arm is 4 months. Assuming accrual of approximately 7 subjects per month for 18 months, 110 PFS events are projected 24 months after the date the first subject is randomized. Approximately 134 subjects may be enrolled to accommodate for up to 10% of subjects who may become lost to follow-up.

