4. PLANNED ANALYSES

The following analyses will be performed for this study:

- Analyses for Independent Data Monitoring Committee (IDMC) meetings
- Main Analysis
- End of Study Analysis

A delivery date and an appropriate data cut-off date will be determined by the study team at least 8 weeks in advance of each planned analysis. Data used for planned analyses are expected to be as clean as possible prior to analysis and extracted with the agreement of the sponsor. The QuintilesIMS Data Management Interim Database Lock Plan for this study will provide detail.

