4.2. MAIN ANALYSIS

The purpose of the Main Analysis is to establish proof of concept for AGS-16C3F in the treatment of RCC, based on efficacy, safety and PK data; and to support preparation of a Clinical Study Report (CSR).

The Main Analysis is planned after approximately 110 PFS events are observed. The data cut-off date for the Main Analysis will be determined based on the primary efficacy endpoint of PFS under the Censoring Rules (Set 1). Data from visits and assessments that occurred prior to or on the cut-off date are expected to be complete and all critical fields are expected to be clean. Data that occurred after the cut-off date yet entered in the EDC prior to data extraction will be excluded from the main analysis.

The planned analyses identified in this SAP will be performed by Quintiles Biostatistics following sponsor authorization of the SAP, sponsor authorization of the analysis sets, and sponsor permission to lock the database. The study Unblinding Plan provides more detail.

PK parameter estimation will be performed by the Agensys pharmacokineticist and is outside the scope of this SAP. However, Quintiles will report the PK concentration results and PK parameter estimates for the Main Analysis as described in this SAP.

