4.3. END OF STUDY ANALYSIS

An End of Study Analysis will be performed at the discretion of the sponsor when any one of the following conditions occurs:

- The IDMC recommends stopping the study
- AGS-16C3F has been either approved or rejected by every country in which subjects were enrolled in the study
- Every randomized subject has met one of the following conditions: (1) the subject has discontinued from the study, or (2) the subject has been followed for a minimum of 12 months after discontinuing treatment, or (3) the subject has been followed for 12 additional months after the planned Main Analysis was performed.

The End of Study Analysis is expected to include safety analyses of AEs and efficacy analyses of the PFS and OS.

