7.4. MULTIPLE COMPARISONS/MULTIPLICITY

Analyses will be performed twice during this study. The main analysis will be conducted and conclusions about efficacy will be made when approximately 110 PFS events have occurred. No adjustment of the alpha used in the Main Analysis will be made due to conducting the End of Study Analysis.

As this is a two-arm study with one primary end point, no adjustment for multiple endpoints or multiple comparisons will be required for the primary analysis.

Since the secondary endpoints do not have a natural hierarchy and there is limited power for these tests, nominal p-values will be reported, which means that no formal adjustment for multiplicity will be done. However, if substantial differences in results among these endpoints are observed, reporting of results will include specific statements acknowledging the increase in type 1 error inherent in situations with multiple comparisons.

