17.1.2.1. PFS Censoring Rules (Set 1)

The PFS Censoring Rules (Set 1) will be used to manage missing data in the primary analysis of PFS. Under the Set 1 rules, PFS will be right-censored for subjects who meet one or more of the following conditions:

- Subjects with no post-baseline disease assessments (unless death occurred prior to the first scheduled assessment, in which case death will be considered a PFS event)
- Subjects who initiate subsequent anticancer therapy or intervention in the absence of documented progression
- Subjects who die or have disease progression after missing 2 or more consecutively scheduled disease assessment visits
- Subjects who are last known to be alive and progression-free on or before the data cut-off date

For such subjects, PFS will be right-censored according to the conventions described in Table E. These conventions are based on the May 2007 FDA Guidance for Industry “Clinical Trial Endpoints for the Approval of Cancer Drugs and Biologics”.

Table E. PFS Censoring Rules (Set 1): Date of Progression or Censoring

Situation	Date of Progression or Censoring	Outcome
Death before first scheduled disease assessment	Actual date of death	Progressed
Documented disease progression before first scheduled disease assessment	Actual date of disease assessment at which progression was noted	Progressed
Death or documented disease progression between 2 scheduled disease assessments	Actual date of death or actual date of first disease assessment showing documented disease progression, whichever occurs first	Progressed
Missed ≥ 2 consecutive disease assessments immediately prior to death or progression	Actual date of last non-missing disease assessment that is before the missed visits and prior to death and prior to documented disease progression	Censored
No death and no post-baseline disease assessments	Actual date of randomization	Censored
Non-protocol anticancer treatment started prior to death or prior to documentation of disease progression	Actual date of last non-missing disease assessment prior to start of non-protocol anticancer treatment	Censored
Alive and not progressed [1]	Actual date of last non-missing disease assessment	Censored

[1] Without death and without documentation of disease progression; includes subjects who may have discontinued from study prior to death and without documentation of disease progression.

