17.1.2.4. PFS Censoring Rules (Set 4)

The PFS Censoring Rules (Set 4) are designed to address possible limitations of the scientific methods used for documentation of disease progression by including symptomatic or non-radiological disease progression as an observed PFS event.

Set 4 rules will be used for sensitivity analyses. Under Set 4 rules, an observed PFS event is defined as clinical (i.e., symptomatic or non-radiological) disease progression, documented disease progression, or death due to any cause. Subjects who do not experience clinical or documented disease progression or death during the analysis period will be censored.

PFS will be right-censored for subjects who meet one or more of the following conditions:

- Subjects with no post-baseline disease assessments (unless death occurred prior to the first scheduled assessment, in which case death will be considered a PFS event)
- Subjects who initiate subsequent anticancer therapy or intervention in the absence of documented progression
- Subjects who die or have disease progression immediately progression immediately after missing 2 or more consecutively scheduled disease assessment visits
- Subjects who are last known to be alive and progression-free on or before the data cut-off date

For such subjects, PFS will be right-censored according to the conventions described in Table H.H These conventions are based on the May 2007 FDA Guidance for Industry “Clinical Trial Endpoints for the Approval of Cancer Drugs and Biologics”.

Table H. PFS Censoring Rules (Set 4): Date of Progression or Censoring

Situation	Date of Progression or Censoring	Outcome
Death before first scheduled disease assessment	Actual date of death	Progressed
Death, documented disease progression or clinical progression between 2 scheduled disease assessments	The earliest of: (1) actual date of death, (2) actual date of first disease assessment showing clinical disease progression, (3) actual date of first disease assessment showing documented disease progression	Progressed
Missed ≥ 2 consecutive disease assessments immediately prior to a PFS event	Actual date of last non-missing disease assessment that is prior to the missed visits and prior to any PFS event	Censored
No death and no post-baseline disease assessments	Actual date of randomization	Censored

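### Could censoring keep the 110-event Main Analysis from ever being triggered with 134 subjects, and does the plan need a written fallback date?

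*Protocol*

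**What the plan says.** Protocol 7.1, the synopsis and SAP 3.5 carry the same sample-size paragraph. It assumes median PFS of 4 and 6 months, a hazard ratio of 0.667, one-sided alpha of 0.1, 110 events for 80% power, accrual of about 7 subjects a month for 18 months, and 110 events at month 24. It ends: "Approximately 134 subjects may be enrolled to accommodate for up to 10% of subjects who may become lost to follow-up".

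SAP 4.2 plans the Main Analysis after approximately 110 PFS events, with a cut-off date "determined based on the primary efficacy endpoint of PFS under the Censoring Rules (Set 1". SAP 7.4 attaches the efficacy decision to that analysis: "The main analysis will be conducted and conclusions about efficacy will be made when approximately 110 PFS events have occurred".

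Set 1 (SAP 17.1.2.1 and Table E, matching Protocol 7.4.1.1 and Table 13) censors subjects with no post-baseline assessment, subjects whose event follows two or more missed assessments, and "Subjects who initiate subsequent anticancer therapy or intervention in the absence of documented progression". Protocol 6.1 also lists this reason for stopping treatment: "Subject develops clinical progression (if objective disease progression is not evaluated". Only under the Set 4 sensitivity rules is it true that "an observed PFS event is defined as clinical (i.e., symptomatic or non-radiological) disease progression".

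On timing, SAP 4 says: "A delivery date and an appropriate data cut-off date will be determined by the study team", at least 8 weeks before each planned analysis. SAP 4.3 adds: "An End of Study Analysis will be performed at the discretion of the sponsor when any one of the following conditions occurs". That analysis includes PFS and does not depend on an event count, but it is not named as a substitute for the Main Analysis.

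**The concern.** An event-driven design keeps its power only if the events can occur. The one stated allowance, 10% lost to follow-up, does not cover the other Set 1 reasons for censoring. In advanced renal cancer, subjects may well stop for symptoms or toxicity and start another drug before a scan shows progression. If enough of them did, 134 subjects could not produce 110 counted events, and the analysis that carries the efficacy conclusion would have no date under the SAP. Someone would then have to pick a cut-off in an open-label trial whose endpoint is read by the investigator. So there seem to be two things at stake: lost power, and a cut-off chosen by people who can see how the trial is going.

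**Working it through.** **Inputs.** From Protocol 7.1: medians 4 and 6 months (exponential), hazard ratio 0.667, one-sided alpha 0.1, power 80%, 110 events, N = 134, 7 subjects a month. Allocation is 1:1 (Protocol 4.4). The share permanently censored, q, is not in the documents and is varied below.

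**1. The plan's own figures.**
- Events (Schoenfeld): 4 × (1.2816 + 0.8416)² / (ln 0.667)² = 109.95, so 110.
- Critical hazard ratio: exp(−2 × 1.2816/√110) = 0.783.
- Difference in medians: 4/0.783 − 4 = 1.1 months.
- Month 24: 134 subjects at 7 a month (19.1 months of accrual) with no loss give 110.2 events. The literal 7 × 18 = 126 subjects give 105.9.

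The design figures all reproduce. The month-24 forecast reproduces if all 134 are enrolled at the stated rate and none are lost.

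**2. The ceiling.** 134 − 110 = 24, and 24/134 = 17.9%. If the full 10% were lost before any event, that would use 13.4 subjects and leave 10.6 (7.9%) for the other Set 1 causes. The trigger is only approximately 110: if 107 events sufficed the limit would be 27/134 = 20.1%, and if 105 sufficed, 29/134 = 21.6%.

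**3. When event 110 arrives.** Accrual is uniform over 18 to 19.1 months. Censoring is modelled in two ways: as a constant hazard, equal in both arms, that eventually censors a share q; or by removing a share q outright. The month ranges span both models and both accrual periods.

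| q | Most events possible, 134 × (1 − q) | Month of event 110 |
|---|---|---|
| 10% | 120.6 | 26.7-29.2 |
| 15% | 113.9 | 31.9-36.5 |
| 17% | 111.2 | 38.6-45.6 |
| 20% | 107.2 | not reached |
| 25% | 100.5 | not reached |
| 30% | 93.8 | not reached |

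**4. Power at a shortfall.** Power = Φ(√d/2 × ln 1.5 − 1.2816). This gives 80.1% at d = 110, 79.3% at 107, 77.2% at 100 and 75.3% at 94.

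**5. What a calendar fallback would deliver.** Suppose the cut-off were month 36, about 18 months after the last randomization.
- Hazard model: 105.5-105.7 events at q = 20%, 99.2-99.4 at 25% and 92.9-93.1 at 30%, each within 2 events of the ceiling.
- Removal model: 103.3-103.7, 96.8-97.2 and 90.4-90.7, which is 3.1 to 3.9 events short of the ceiling. Power at 90.4 events is 74.1%.
- At q = 17% the fallback would stop at 107.2-109.4 events, although 110 could still be reached at months 38.6-45.6.

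**6. What counts as permanent censoring.** Three readings bear on how likely a shortfall is.
- Subjects still event-free at the cut-off do not use up the 24. The cut-off moves with the event count, so they affect only the date.
- Clinical progression is not a censoring row in Table E. Such subjects continue 8-weekly scans until progression, new therapy or death (Protocol 5.5), and they are lost to the count only if another row applies.
- SAP 17.1.2 says that where several situations fit one subject, an event outranks censoring. Read literally, this would turn some events after missed visits or new therapy back into counted events. It sits awkwardly with Table E, but it can only lower the censoring share.

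**The case for a change.** The best case for a change is that a fallback is nearly free. One sentence in SAP 4.2 and 7.4 would fix the date before anyone could be tempted by the data, with no change to N, alpha or the test. SAP 4.3 does not fill the gap, because it is discretionary and SAP 7.4 reserves efficacy conclusions for the 110-event analysis. Delay also starts well below the 17.9% limit: at 15% permanent censoring, event 110 comes at about month 32 to 36.5, against a forecast of 24.

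Some of this stands. No shortfall rule is written, the 10% allowance covers one cause only, and month 24 is optimistic once losses occur. The rest is weaker. The choice of cut-off is not as open as it looks: SAP 4 has the date set at least 8 weeks ahead, SAP 4.2 ties it to Set 1 PFS, and Protocol 7 requires departures from the SAP to be justified in the study report. Setting the date ahead does not blind an open-label study team, but it does prevent a cut-off picked after the analysis is seen. A fixed calendar date has its own cost, since it could stop the trial a few events early when 110 was still within reach.

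**Conclusion.** No change is needed. The ceiling is correct arithmetic, but it is not an error in the plan: every design figure reproduces, and the trigger and the enrolment target are both approximate. A shortfall requires permanent Set 1 censoring above about 18-20%. That is an assumption, because the documents give no expected rate and the precedence rule in SAP 17.1.2 could reduce it. If it happened, the study would lose at most a few points of power: 75-79% at the event ceilings for 20-30% censoring, or about 74% at the least favourable month-36 count, in a phase 2 proof-of-concept trial tested at one-sided 0.1.

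What remains is an unwritten contingency. A competent team facing a stalled count would set a cut-off in advance, run the same test once and report the events obtained. Spelling out the assumptions behind month 24 would add detail to a forecast that does not determine when the analysis takes place. With 10% permanently censored, readers should expect 110 events nearer months 27 to 29. These figures rest on exponential PFS at the planned medians, uniform accrual and the same censoring process in both arms.
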